## **Subjects Study Visits**

### **Welcome Subject and Consent**

A research staff member who is currently trained in human subjects will greet the subject, and complete an eligibility inclusion/ exclusion form, and perform the consent process. Potential subjects are given the IRB-approved consent form to read and are provided the opportunity to ask questions about the study.

If any subject does not meet the requirement, they will not be screened further and will be thanked for their time.

If the potential subject does meet the requirement, study procedures may begin.

### **Enrollment**

As part of study participation, each subject will be assigned a Subject ID number. This Subject ID number will be maintained throughout the study. The subject ID number which was assigned to them will not be re-used.

### **Study Visits**

A dental examiner will review their eligibility questionnaires, ask any additional questions to clarify eligibility, and perform an intraoral evaluation which will determine eligibility and provide an initial baseline of the intraoral cavity prior to in-mouth use of the test product.

#### **Visit 1: May be combined with visit 2 if subject has abstained from brushing, flossing and mouthwash for 24 hours**

- Demographic information
- Medical history taken
- A dental examiner will perform an intraoral evaluation. The oral cavity will be evaluated and assessed for any abnormalities that may interfere with the brushing procedure, such as oral piercings.
-

---

- Instructions given to abstain from brushing, flossing, gum or mouthwash for 24 hours prior to visit 2
- Gift card dispensed
- Schedule next visit

### **Visit 2:**

- Review Inclusion / Exclusion Questionnaire
- Randomization
- Pre-brushing Intraoral Evaluation and plaque index
- Intraoral photographs pre-brushing
- Verbal review of brushing instructions
- Supervised and Timed Brushing with assigned products
- Dental examiner performs post- brushing intraoral evaluation and plaque index
- Intraoral photographs post-brushing
- Subject questionnaire
- Gift card dispensed

### **Randomization**

Subjects will be randomized with a subject identification number throughout their study visits. A randomization table will be used by study staff to determine if the subject is a test or control brush.

### **Product Use**

Subjects will be given verbal brushing instructions for the test or control brush.

For the control group, the toothbrush bristles will be dampened with water and toothpaste, will be pre-dispensed (on a clean surface) by the study staff to assure that all subjects are given the same quantity of toothpaste and to assure that the proper amount of toothpaste will be given. The same toothpaste will be provided to all the subjects. The subject will use the device directly over the sink.

Subjects will be reminded of the brushing instructions and will be timed during their brushing.

For the test group, the mouthpiece will be inserted by patient under the supervision of the study staff. The subject will use the device directly over the sink. If the subject is having any difficulty or uncomfortable, the in-mouth testing will be stopped immediately and reported to the Principal Investigator.

### **Assessment of Safety and Adverse Event Reporting**

#### **Definitions**

**Adverse Events (AEs) and Serious Adverse Events (SAEs) are defined by the ICH Guideline for Good Clinical Practice (ICH GCP) as follows:**

Adverse Event: Any untoward medical occurrence in a patient or clinical investigations subject administered a pharmaceutical product and which does not necessarily have to have a causal relationship with this treatment. An adverse event
---

---

(AE) can therefore be any unfavorable and unintended sign (including abnormal laboratory finding), symptom, or disease temporally associated with the use of a medicinal product, whether or not considered related to the medicinal product.

AEs include any clinically significant deterioration of a subject's medical status, after enrolled and signing an Informed Consent Form. The AE may involve any organs or systems and can be represented by the new onset or the deterioration of a disease, a syndrome, a symptom, a physical sign, as well as by findings and results of instrumental examinations and laboratory tests. Any medically relevant and untoward change from baseline, including frequency or pattern changes for a fluctuating condition (e.g., migraine), occurring after enrollment. All such occurrences must be recorded and reported accordingly, whether they appear causally related to the study product, or not.

**Serious Adverse Event:** Any adverse event occurring at any dose that results in any of the following outcomes:

- Death
- Life threatening adverse event
- Inpatient hospitalization, or prolongation of existing hospitalization
- Persistent or significant disability/incapacity
- Congenital anomaly/birth defect

Important medical events that may not result in death, be life-threatening, or require hospitalization may be considered a serious adverse experience when, based upon appropriate medical judgment, they may jeopardize the patient or subject and may require medical or surgical intervention to prevent one of the outcomes listed in this definition.

## Documenting and Reporting Adverse Events

### General Procedures for All Adverse Events

All clinical complaints, symptoms, or signs that meet the adverse event definition will be recorded on the Adverse Reaction Form using a recognized medical term or diagnosis that accurately reflects the event. Source documentation should be maintained that allows for clear identification of each adverse event and the following parameters required for the form:

- AE description
- Date of onset
- Date of resolution
- Outcome
- Severity
- Seriousness
- Relationship to study product (causality)
- Actions taken

Adverse events will be assessed by the investigator or designee for severity, relationship to the study intervention, possible etiologies, and whether the event meets the criteria as a serious adverse event and therefore requires immediate notification of the sponsor.

---

For data collection purposes, the outcome of all adverse events recorded on the Adverse Reaction Form will be designated as of the completion of the final evaluation or examination. However, the investigator is responsible for following all adverse events until resolution or until no longer of clinical concern and providing these data to the sponsor.

### **Baseline and Post-use Safety Evaluation**

Participant safety shall be monitored from the time each participant signs the Informed Consent Form until conclusion of the study. Participant safety shall be monitored to detect any deviations in the medical health or dental status present at baseline.

### **Device Deficiencies**

All device deficiencies use or user errors, and equipment failures will be documented. Use or user errors will be captured as part of the source documentation

### **Statistical Analysis Plan**

Multiple sites within each subject will be evaluated using a Turesky Modification of the Quigley-Hein Plaque Index at the treatment visit both before and after brushing.

To assess the device effect after brushing, a paired t-test will be applied on the change outcome. An unpaired t-test will be used to compare the efficacy of both devices. A visual analog assessment will be done will be done on all subjects. The number and percentage of reactions related to each brushing method will be collected and the final tolerance score estimated.

The selection of 60 participants is expected to identify statistically significant differences in clinical parameters before and after brushing among the subjects of the study. The power analysis was based upon a recent study by Klonowicz et al in which a significant reduction of plaque was achieved after brushing of  $p<0.05$ .

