## **Study Design:**

This is 2 visit, single-blinded, randomized controlled clinical trial.

All subjects will sign an Institutional Review Board (IRB)-approved informed consent form before any study procedures may be performed. This study will be completed according to applicable Good Clinical Practices and the Declaration of Helsinki.

This study includes

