## **Risk and Benefit Analysis**

The subject may be uncomfortable with another person watching them brush or experience some bleeding or sensitivity during this brushing procedure. All procedures conducted in the brushing procedure are like what is experienced during a routine tooth brushing. The examiner will perform a thorough pre intraoral evaluation to check for any type of abnormal abrasion or wound in the mouth. If there is any predisposing condition in the subject's mouth, the dental examiner will inform the subject and may recommend the subject not participate in the study. The risk of permanent harm or injury, or disability as a result of participation in this research study is minimal. Participation is not expected to cause any oral conditions different from those normally experienced in routine brushing with a manual toothbrush. There is a chance that use of the research study products may involve risks that are currently unknown. The subject will be asked to report any discomfort or irritation that may be experienced while using research study products.

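### The tolerance result appears to count only reactions related to the brushing method; it should count all reactions by randomised arm, because nothing says that the person assigning relatedness is blinded

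*Protocol*

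**What the plan says.** The only analysis text on reactions or tolerance in either document is one sentence in the protocol's Statistical Analysis Plan section: "The number and percentage of reactions related to each brushing method will be collected and the final tolerance score estimated". No test, denominator or definition of the score follows. The separate SAP covers plaque scores, overall and by dentition, and does not mention reactions, tolerance or abrasion.

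Data collection is wider. On untoward changes after enrolment, the adverse event Definitions state: "All such occurrences must be recorded and reported accordingly, whether they appear causally related to the study product, or not". Under General Procedures for All Adverse Events, each event goes on a form with a causality field, and "Adverse events will be assessed by the investigator or designee for severity, relationship to the study intervention".

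On blinding, Study Design says only: "This is 2 visit, single-blinded, randomized controlled clinical trial". The blinded party is not named. Under Randomization, study staff use the allocation table; under Product Use, they supervise the test device. The test-group paragraph of Product Use adds that, if the child has difficulty or discomfort, "the in-mouth testing will be stopped immediately and reported to the Principal Investigator". The control-group paragraph has no matching instruction.

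**The concern.** In a randomised trial the control arm already shows how many reactions would occur without the test device. A comparison of all reactions by arm uses that directly. Keeping only reactions that someone attributes to the brushing method puts a judgement between the randomisation and the result. If that person knows or guesses the arm, the judgement can differ between arms.

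The protocol's own framing makes this plausible. The Risk and Benefit Analysis takes the control treatment as its benchmark for what is expected: "Participation is not expected to cause any oral conditions different from those normally experienced in routine brushing with a manual toothbrush". Bleeding after a manual brush could be passed over as ordinary while the same bleeding after an unfamiliar mouthpiece is called related, or it could be treated as ordinary in both. Differential attribution could therefore create a tolerance difference or hide one. As the SAP says nothing on the subject, this one sentence governs the whole tolerance result.

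**Working it through.** **1. Plan's own figure.** There is none to reproduce. The protocol gives 60 children, 30 per arm, justified by the before-and-after plaque difference. The SAP gives N=40 without the split by arm. Neither gives a reaction rate.

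**2. The passages side by side.**
- Recorded: all events, whatever their cause (Definitions).
- Reported for tolerance: reactions related to each brushing method (Statistical Analysis Plan section of the protocol).
- Who decides relatedness: the investigator or a designee (General Procedures for All Adverse Events).
- Is that person blinded? Not stated. Stopped test-device use is reported to the Principal Investigator (Product Use), which identifies the arm for those events only. Bleeding or abrasion found at the post-brushing examination does not follow that route.

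**3. How attribution changes the percentages.** Let r be the true reaction rate and a the probability that a reaction is called related. The reported rate in an arm is r × a. With equal r in both arms, the spurious difference is r × (a_test − a_manual).

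Assumed values: r = 0.20, a_test = 0.90, a_manual = 0.50.
- Test: 0.20 × 0.90 = 0.18.
- Manual: 0.20 × 0.50 = 0.10.
- Spurious difference: 8 points, ratio 0.90/0.50 = 1.8.
- With 30 per arm, 6 versus 6 true reactors would be reported as 5.4 versus 3.0 on average. With 20 per arm (an even split of the SAP's 40, assumed), 4 versus 4 would be reported as 3.6 versus 2.0.

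**4. Range.** The table uses exact enumeration of a two-sided Fisher test at 0.05 with equal true rates. The plan names no test for reactions, so this only gauges scale.

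| True rate, both arms | Difference, 90% v 50% | Falsely significant: all counted, 30/arm | 90% v 50%, 30/arm | 90% v 30%, 30/arm | 90% v 50%, 20/arm |
|---|---|---|---|---|---|
| 10% | 4 points | 0.9% | 1.2% | 2.1% | 1.1% |
| 20% | 8 points | 2.2% | 6.3% | 14.3% | 5.2% |
| 30% | 12 points | 2.6% | 12.7% | 31.3% | 8.7% |
| 50% | 20 points | 2.7% | 27.2% | 64.5% | 17.9% |

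**5. Bias in the other direction.** Take true rates of 40% (test) and 20% (manual), with attribution of 50% and 100%. Reported rates are 0.40 × 0.50 = 20% and 0.20 × 1.00 = 20%. With 30 per arm, the chance of a significant result falls from 29.8% to 2.2%.

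**6. Where there is no spurious difference.** If a is the same in both arms (for example 50% each) and the true rates are equal, the expected difference is zero. Counting all reactions gives the same protection without relying on equal attribution.

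**The case against.** The strongest reply is that the sentence does not say that relatedness is judged. Reactions related to each method could simply mean reactions tabulated by arm, and the sentence does not refer to the causality field. That reading is possible and cannot be excluded. But the two readings give different counts, so the wording needs repair either way.

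A reader might infer that the tolerance comparison necessarily rests on unblinded attribution. The documents do not show that. The blinded role is not named, and a blinded examiner could be the designee. The route to the Principal Investigator covers only stopped test-device use. No formal between-arm test of reactions is planned. The secondary objective on soft tissue abrasion, served by the post-brushing examination, does not depend on relatedness. What remains is that percentages by device will be read side by side, and that neither document specifies an analysis of the abrasion objective.

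A reader might also infer that mild findings are lost because adverse events are confined to clinically significant deterioration. The Definitions say that events include such deterioration; the basic definition covers any unfavourable and unintended sign or symptom.

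Finally, the rates in the illustration are assumed. At a 10% reaction rate the effect on a test would be negligible, and at 20% with 90% versus 50% attribution it is modest.

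**Conclusion.** The point stands as an avoidable exposure to bias in a descriptive safety result. On its natural reading the plan reports a subset of the recorded reactions, selected by a judgement that neither document says is blinded, so the percentages by device can be distorted by differential attribution. That this would happen is not shown.

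The size cannot be estimated from the documents. In the illustrations the spurious difference with 90% versus 50% attribution runs from 4 to 20 points for true rates of 10% to 50%, and it is nil if attribution is equal. These figures rest on assumed reaction rates, attribution probabilities and a Fisher test.

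The primary plaque result is not touched. It would go too far to require that the tolerance score be built from the all-reaction count. The score is undefined and could come from another source, such as the visual analog assessment or the subject questionnaire.

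**What to change.** Replace the reactions part of the sentence in the protocol's Statistical Analysis Plan section, and carry it into the SAP, with text such as: *The number and percentage of children with any new or worsened oral soft-tissue finding or complaint from the start of brushing will be reported by randomised arm, regardless of judged relationship. Reactions judged related will be given in a supplementary listing.*

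Report early stopping of brushing separately, for both arms, outside this count. The Withdrawal Criteria section already asks for the reason for discontinuation in any child. The stopping instruction in Product Use appears only in the test-group paragraph, so stops may be picked up unequally and should not be mixed into the count.

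The cost is one sentence and one table. The inputs are already planned in both arms: intraoral evaluation before and after brushing, reported discomfort, and recording of events whatever their cause. The small downside is that coincidental findings add a little noise to both arms. The change does not correct unequal detection or reporting between arms. It helps to state who is blinded and who assigns relationship, so that a reader can judge what remains.

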### **Access to Source Data**

This study will collect data on the performance of the study device. The data will be used without any personally identifiable information will be stored in the case report forms and entered into a spreadsheet for statistical analysis.

### **Case Report Forms**

Data collection is the responsibility of the clinical trial staff at the site under the supervision of the site investigator. The investigator is responsible for ensuring the accuracy, completeness, legibility, and timeliness of the data reported. Only staff that have been delegated by the Principal Investigator will be able to enter or make changes to data in the study documentation.

---

## **Study Confidentiality**

Study records, including each subject's signed consent form and eligibility, and other study-related documents pertaining to the conduct of the study shall be kept in a secure area. Confidentiality shall be maintained. The results of this research project may be presented at meetings or in publications; however, subject identity will not be disclosed in such publications.

## **Subject Confidentiality**

Subjects enrolled in the study shall be assigned a Subject ID number. All recorded data are then entered per the unique Subject ID. Subject information shall remain confidential. However, consent forms that identify subjects may be inspected by the sponsor, its authorized designees and regulatory agencies including but not limited to, the Department of Health and Human Services (DHHS), the United States Food and Drug Administration (FDA) and other foreign regulatory bodies. Because of the need to release information to these parties, absolute confidentiality cannot be guaranteed. Only authorized personnel associated with the conduct and/or review of the study and the resultant data shall have access to information that links subject identifiers to the corresponding assigned study code. Disclosure of subject information to personnel other than those permitted by study staff, its designees or representatives, or appropriate regulatory agencies is prohibited.

## **Risk and Benefit Analysis**

The subject may be uncomfortable with another person watching them brush or experience some bleeding or sensitivity during this brushing procedure. All procedures conducted in the brushing procedure are like what is experienced during a routine tooth brushing. The examiner will perform a thorough pre intraoral evaluation to check for any type of abnormal abrasion or wound in the mouth. If there is any predisposing condition in the subject's mouth, the dental examiner will inform the subject and may recommend the subject not participate in the study. The risk of permanent harm or injury, or disability as a result of participation in this research study is minimal. Participation is not expected to cause any oral conditions different from those normally experienced in routine brushing with a manual toothbrush. There is a chance that use of the research study products may involve risks that are currently unknown. The subject will be asked to report any discomfort or irritation that may be experienced while using research study products.

## **Anticipated Clinical Benefits**

Participation in this trial may not result in direct benefit to the subject. The information collected from subjects will be used to improve future product design and function.

## **Compensation**

---

Participants in this study will receive up to \$50 in gift cards for their participation. A \$25 gift card will be given at the end of each visit. No therapeutic or other benefit will be received by participating in the study.

Study title: Efficacy of a Novel Brushing Device

NCT #: NCT05038293

PI Name: [name]

Document Name: Statistical Analysis Plan

Approval Date: May 14, 2021

Please find the attached statistical analysis used for this study.

Statistical Analysis Plan

The proposed clinical study is a Single-blinded, randomized controlled clinical trial in humans designed to assess compare the effects the test brushing device versus a manual toothbrush.

Primary outcome analysis plan: Oral health status and plaque accumulation was measured and obtained through clinical examination. The Turesky modification of the Quigley-Hein Index was used to quantify the amount of dental plaque on six assigned index tooth sites in children (ages 5-17; N=40) prior to and after use of the assigned oral hygiene device. Individual tooth plaque scores were then averaged within device group pre and post brushing and reported (mean \pm sd). Data was assessed for normality using the *rnorm()* function within the “stats” package within R Statistical Software. Difference in mean plaque data within and between device groups pre and post brushing was then evaluated using the parametric *t.test()* function and adjusted for multiple testing by False Discovery Rate (FDR) with an *alpha* of 0.05 (95% CI) using the “rstatix” package within R Statistical Software.

Secondary outcome analysis plan: Dentition status (primary, mixed, permanent) was recorded through clinical examination. Data from the primary outcome (Plaque score using the Turesky modification of the Quigley-Hein Index) was then stratified to determine the impact of dentition status on outcomes between device groups. Individual tooth plaque scores were stratified by Dentition status (primary: N = 2; mixed: N = 27; permanent: N = 11) and then averaged within device group pre and post brushing and reported (mean \pm sd). Difference in mean plaque data within and between device groups and by dentition status pre and post brushing was then evaluated using the parametric *t.test()* function and adjusted for multiple testing by False Discovery Rate (FDR) with an *alpha* of 0.05 (95% CI) using the “rstatix” package within R Statistical Software.

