## Study Overview

Study Overview	
Subjects	Recruit 60 subjects. Each subject will make 1-2 visits. The entire study is estimated to take approximately 6 months.
Inclusion/Exclusion Criteria	
Potential subjects will be given a checklist of the inclusion and exclusion criteria to determine if they are eligible to participate. A study staff will confirm the eligibility by the "yes" and "no" responses accordingly.
 
Inclusion Criteria (All answers should be yes):
 
 
• Between the ages of 5-17
 
• In good general health
 
• Fluent in English
 
• Parent or guardian willing and able to provide written informed consent
 
• Have 16 scorable teeth (non crown/bridge/or full amalgams)
 
• Have had a dental cleaning and exam in the past 24 months
 
 
Exclusion Criteria (To qualify, all answers must be no):
 
 
• Have advanced periodontal disease or severe gum disease
 
• Have mouth or teeth pain that prevents brushing in any areas
 
• Have intraoral piercings (tongue or lip) that cannot be removed
 
• Have non-controlled diabetes
 
• Have any autoimmune or infectious disease or any medical condition that would delay wound healing
 
• Have untreated visible cavities or untreated dental work
 
• Had oral or gum surgery in the previous 2 months
 
• Take antibiotic premedication for dental procedures
 
• Undergoing or require extensive dental or orthodontic treatment
 
• Current smoker
 
• Generalized recession over 1mm
 

Study Objectives	To compare plaque removal efficacy of an automated mouthpiece-based toothbrush to a manual toothbrush, and to assess effect on oral soft tissues.
Study Design	
 
• Single Site
 
• Parallel Design
 
• 60 Subjects stratified by dentition (primary, mixed, and permanent) are randomized evenly to 2 treatment groups
 
• Randomized, blinded, 2 treatment groups
 

Study Duration	
 
• 2 visits
 
• Each study visit will take approximately 90 minutes
 

Study Devices	
List of Devices:
 
Primary Investigation: (All 60 subjects)
 
 
1. Automated brush: 30 subjects
 
2. Manual toothbrush: 30 subjects
 

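### The SAP names no unit of analysis for its t-tests on six sites per child; separately, the device test in the two-child primary-dentition stratum has no valid result, and rnorm() does not check normality

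*SAP*

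**What the plan says.** The primary outcome paragraph of the SAP says the plaque index was "used to quantify the amount of dental plaque on six assigned index tooth sites in children (ages 5-17; N=40". It gives one averaging step: "Individual tooth plaque scores were then averaged within device group pre and post brushing and reported" as mean and SD. On distribution it says "Data was assessed for normality using the *rnorm()* function". The test sentence is "Difference in mean plaque data within and between device groups pre and post brushing was then evaluated using the parametric" t.test() function, with a false discovery rate (FDR) adjustment at alpha 0.05.

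The secondary outcome paragraph repeats the pattern by dentition: "Individual tooth plaque scores were stratified by Dentition status (primary: N = 2; mixed: N = 27; permanent: N = 11". Its test sentence reads "Difference in mean plaque data within and between device groups and by dentition status pre and post brushing was then evaluated using the parametric"; the R function named is again t.test(). The stratum of two is not exempted.

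The unit of allocation is the child. The Protocol's Study Overview says "60 Subjects stratified by dentition (primary, mixed, and permanent) are randomized evenly to 2 treatment groups", and its Randomization section says "A randomization table will be used by study staff to determine if the subject is a test or control brush". The Protocol's Statistical Analysis Plan section has several sites scored per subject before and after brushing. It plans a paired t-test on the change and an unpaired t-test between devices. It does not say how several sites become one observation.

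**The concern.** Six scores from one mouth come from one brusher in one session and are likely to be correlated. The wording allows three analyses:

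- **(a)** all tooth scores pooled as separate observations;
- **(b)** one mean per child;
- **(c)** a separate test for each index tooth across children, with FDR over the teeth.

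Under (b) or (c) the error rate is sound and the gap is one of reporting. Under (a) correlated scores count as independent, the standard error is too small, and chance differences between devices are declared too often. FDR does not repair this, because it deals with the number of tests and not with dependence within a mouth. As it stands, a reader cannot tell which analysis an SD, p-value or confidence interval belongs to.

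Two further items need correcting whichever reading holds: a between-device t-test in a stratum of two children, and a normality check assigned to a random-number generator.

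**Working it through.** **Inputs from the SAP.** 40 children and six sites per child. The strata are 2 + 27 + 11 = 40, so every N counts children and N = 2 means two children. At six scores each there are 40 × 6 = 240 scores per time point.

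**Assumptions.** There are 20 children per arm (the SAP gives only N = 40; the Protocol plans even allocation). All six scores are available in every child. The within-child correlation (ICC) is 0.05 to 0.7, since neither document gives a value. There is no device effect.

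**Main comparison.** With six scores per child the design effect is DE = 1 + (6 − 1) × ICC. Pooling teeth understates the standard error by a factor √DE, so a nominal 5% test rejects at the rate 2 × [1 − Φ(1.96/√DE)]. For ICC 0.3: DE = 2.5, √DE = 1.58, 1.96/1.58 = 1.24, rate 21.5%. The effective number of scores is 240/2.5 = 96. The simulated column comes from 40,000 null trials with Welch t-tests.

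| ICC | DE | √DE | Formula, pooled teeth | Simulated, pooled teeth | Tooth SD ÷ child-mean SD |
|---|---|---|---|---|---|
| 0.05 | 1.25 | 1.12 | 8.0% | 8.0% | 2.19 |
| 0.1 | 1.5 | 1.22 | 11.0% | 11.1% | 2.00 |
| 0.2 | 2.0 | 1.41 | 16.6% | 16.6% | 1.73 |
| 0.3 | 2.5 | 1.58 | 21.5% | 22.1% | 1.55 |
| 0.5 | 3.5 | 1.87 | 29.5% | 29.9% | 1.31 |
| 0.7 | 4.5 | 2.12 | 35.6% | 36.0% | 1.15 |

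In the same simulations child means reject 4.7% to 5.2%. Tests per tooth reject 4.9% to 5.0% each, and 3.7% to 5.0% for any of six after Benjamini-Hochberg adjustment. The last column is √(6/DE): the reported SD also depends on the unit.

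**Change scores.** For tooth-level changes the relevant ICC is that of the changes. Over the same range, pooled teeth reject 7.9% to 36.6% and child-mean changes 4.8% to 5.2%.

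**Effect of FDR.** The SAP does not list its family of tests. Assume four (between devices before and after brushing, and before versus after within each device), a brushing effect of 1 SD and a pre-post correlation of 0.5. The post-brushing device test then rejects 6.8% to 34.6% with pooled teeth and 3.7% to 4.0% with child means.

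**Primary-dentition stratum, N = 2.** The split by device is not given.

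- *One child per device, child means or per tooth:* each arm has one observation. R's t.test() stops with an error that there are not enough observations, both with Welch and with equal variances.
- *Both children on one device:* there is no comparator under any reading.
- *One child per device, pooled teeth:* six scores against six return a p-value, but child and device are completely confounded. With no device effect this test rejects 7.5%, 10.8%, 18.1%, 25.7%, 40.7% and 56.8% at the six ICC values above (100,000 trials).

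**Normality check.** rnorm() takes a count, a mean and an SD. Given a vector of 40 values in R, it returned 40 new random numbers and no statistic about the data.

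**The case against.** The best defence is that the child is the natural reading. Every N in the SAP counts children. The Protocol sizes the trial in participants and plans a paired test on the change. Its Study Summary and Visit 2 list speak of a plaque score or index before and after brushing, as if each child has one. The SAP's averaging sentence describes the reported mean and SD, not the test. With six scores in every child, the mean of all teeth equals the mean of the child means, so that sentence fits either unit.

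Much of this stands. A reader might infer from the averaging sentence that teeth were pooled and that the reported p-values are therefore too small. The documents do not support that step, and the 8% to 36% applies only if pooling took place. But none of the text cited in defence states the unit: a paired test can be run on teeth as readily as on children, and a count of participants does not say what entered t.test(). The SAP describes the analysis as done, so this should be stated.

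The ICC, the even split and the six complete scores per child are also assumptions. That is why a range is shown. Nothing in the documents allows it to be narrowed, for change scores or otherwise.

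**Conclusion.** The unit of analysis is not stated; that follows directly from the text. The size of the consequence is conditional: about 8% to 36% false positives at nominal 5% if teeth were pooled, under the assumptions above, and about 5% if child means were used. The gap should be corrected in either case, and it becomes a serious error in the primary analysis if pooling is confirmed.

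The device test in the two-child stratum has no valid result under any reading. A reader might go further and say it cannot be run at all. That is too strong, since pooled teeth at a one-to-one split do produce a p-value, though not a usable one.

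The rnorm() sentence is a minor correction and may be a clerical slip. A reader might infer that the choice of a parametric test rests on a failed check. The documents do not say so: the Protocol already plans t-tests with no normality condition, and the SAP states no rule linking the check to the test. Neither this item nor the two-child stratum adds weight to the question about the primary analysis.

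**What to change.** 1. State in the SAP that each child's scored sites are averaged to one pre-brushing and one post-brushing score, and that the child is the unit for every mean, SD, test and confidence interval. A mixed model with a random child effect is an acceptable alternative. If tests were run per index tooth, say so and state how six results lead to one primary conclusion.
2. Drop the t-tests in the primary-dentition stratum. List the two children's individual values by device, with no SD or p-value; with one child in an arm, a child-level SD is undefined.
3. Replace rnorm() with a Q-Q plot or Shapiro-Wilk test of the child-level changes or residuals.

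**Cost.** If child means were used, only text changes, together with removal of the tests in the stratum of two. If teeth were pooled, the existing data must be re-run. Standard errors then grow by √DE, about 1.1 to 2.1 times over the assumed ICC range, and p-values become less favourable. No new data are needed.
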